### 9.4.3 ANALYSIS OF THE SECONDARY ENDPOINT(S)

The levels of inflammatory markers measured at each time point after induction of hypothermia will be compared to baseline using the Wilcoxon rank sum test.

#### 9.4.4 SAFETY ANALYSES

Safety endpoints will be reported as summary statistics.

9.4.5 N/A	BASELINE DESCRIPTIVE STATISTICS
9.4.6 N/A	PLANNED INTERIM ANALYSES
9.4.7 N/A	SUB-GROUP ANALYSES
1	TABULATION OF INDIVIDUAL PARTICIPANT DATA is a pilot study, individual participant data will be listed by measure and time point.

### 9.4.9 EXPLORATORY ANALYSES

N/A

### **10 SUPPORTING DOCUMENTATION AND OPERATIONAL CONSIDERATIONS**

#### 10.1 REGULATORY, ETHICAL, AND STUDY OVERSIGHT CONSIDERATIONS

### **10.1.1 INFORMED CONSENT PROCESS**

# 10.1.1.1 CONSENT/ASSENT AND OTHER INFORMATIONAL DOCUMENTS PROVIDED TO PARTICIPANTS

All study related activities conducted at participating site, North Shore University Hospital, will be regulated by one local Institutional Review Board titled Northwell Health, IRB. The Federalwide Assurance (FWA) number is 00002505; this documentation demonstrates the commitment to the Federal Department of Health and Human Services (DHHS) and the Office of Human Research Protections (OHRP) indicating that our Health System and the IRB functions in compliance with the federal regulations governing research with human subjects. All investigators involved in this clinical trial will conduct research within the ethical standards recited in the Belmont Report.

Consent forms describing in detail the study intervention, study procedures, and risks are given to the participant and written documentation of informed consent is required prior to starting intervention/administering study intervention. The following consent materials are submitted with this protocol

Informed Consent Form Enrollment /Process Note

In accordance with Northwell Health Consent policy and in adherence to ICH GCP, the Investigator will have IRB written approval for the protocol and the written informed consent form to be provided to the participant. Informed consent will be obtained orally by the IRB approved primary or co-investigator via telephone conversation with the patient's health care proxy or designated next-of-kin who serves as the research participant's legally authorized representative (LAR). Consent will be verified via telephone by the primary clinician with a witness. Given the circumstances surrounding the COVID-19 pandemic, family members are prohibited from physically entering the hospital. Therefore, Informed consent is to be obtained from LAR via telephone process.

#### **10.1.1.2 CONSENT PROCEDURES AND DOCUMENTATION**

Informed consent is a process that is initiated prior to the individual's agreeing to participate in the study and continues throughout the individual's study participation. Consent forms will be Institutional Review Board (IRB)-approved and the participant will be asked to read and review the document. The investigator will explain the research study to the participant (or LAR) and answer any questions that may arise. A verbal explanation will be provided in terms suited to the participant's (LAR) comprehension of the purposes, procedures, and potential risks of the study and of their rights as research participants. Participants (or LAR) will have the opportunity to carefully review the written consent form and ask questions prior to signing. The participant (or LAR) will sign the informed consent document prior to any procedures being done specifically for the study. Participants must be informed that participation is voluntary and that they may withdraw from the study at any time, without prejudice. A copy of the informed consent document will be given to the participants for their records. The informed consent process will be conducted and documented in the source document (including the date), and the form signed, before the participant undergoes any study-specific procedures. The rights and welfare of the participants will be protected by emphasizing to them that the quality of their medical care will not be adversely affected if they decline to participate in this study.

Given the circumstances surrounding the COVID-19 pandemic, family members are prohibited from physically entering the hospital. Informed consent will be obtained from the participants' LAR via telephone by an IRB approved and authorized investigator. The telephone consent process will be witnessed by another personnel member, either from the clinical team or the research team.

A copy of the consent form will be sent via email to the LAR. The LAR will be instructed to respond via email authorizing subject enrollment into the study. When the LAR has an opportunity to print and sign the informed consent, they will be instructed to do so and email it back to Investigator and regulatory lead coordinator.

# 10.1.2 STUDY DISCONTINUATION AND CLOSURE

This study may be temporarily suspended or prematurely terminated if there is sufficient reasonable cause. Written notification, documenting the reason for study suspension or termination, will be provided by the suspending or terminating party to study participants or investigator. If the study is prematurely terminated or suspended, the Principal Investigator (PI) will promptly inform study participants, the Institutional Review Board (IRB), and will provide the reason(s) for the termination or suspension. Study participants will be contacted, as applicable, and be informed of changes to study visit schedule.

Circumstances that may warrant termination or suspension include, but are not limited to:

- Determination of unexpected, significant, or unacceptable risk to participants
- Demonstration of efficacy that would warrant stopping
- Data that are not sufficiently complete and/or evaluable
- Determination that the primary endpoint has been met
- Determination of futility

Study may resume once concerns about safety, protocol compliance, and data quality are addressed, and satisfy the IRB.

# 10.1.3 CONFIDENTIALITY AND PRIVACY

Participant confidentiality and privacy is strictly held in trust by the participating investigators, their staff, and the sponsor(s) and their interventions. This confidentiality is extended to cover testing of biological samples and genetic tests in addition to the clinical information relating to participants. Therefore, the study protocol, documentation, data, and all other information generated will be held in strict confidence. No information concerning the study or the data will be released to any unauthorized third party without prior written approval of the sponsor and/or Principal Investigator, as the sponsor of this study is the Department of Cardiothoracic Surgery of Northwell Health.

All research activities will be conducted in as private a setting as possible.

The study monitor, the study team, other authorized representatives of the sponsor, representatives of the Institutional Review Board (IRB), and any other regulatory agency, such as the Office of Research Compliance, may inspect all documents and records required to be maintained by the investigator, including but not limited to, medical records (office, clinic, or hospital) and pharmacy records for the participants in this study. The clinical study site will permit access to such records.

The study participant's contact information will be securely stored at the clinical site for internal use during the study. At the end of the study, all records will continue to be kept in a secure location for as long a period as dictated by the reviewing IRB, Institutional policies, or sponsor requirements.

Study participant research data, which is for purposes of statistical analysis and scientific reporting, will be transmitted to and stored at the Department of Cardiovascular and Thoracic Surgery at North Shore University Hospital, [name]. This will not include the participant's contact or identifying information. Rather, individual participants and their research data will be identified by a unique study identification number. The study data entry and study management systems used by clinical sites and by North Shore University Hospital research staff, assigned to the Department of Cardiovascular and Thoracic Surgery, will be secured and password protected. At the end of the study, all study databases will be de-identified and archived at the Department of Cardiovascular and Thoracic Surgery Hospital, [name].

Data collected for this study will be captured and stored on case report forms created for this study and entered into the electronic data capture system of REDCap. There will be no identifiers stored on paper. All patient identifiers will be removed. Once enrolled, patients will be assigned a research ID number, beginning with subject number 01, 02, 03 etc. Data will be stored in Northwell REDCap, a compliant database that is a secure web based application used for building and managing trials; it is 21 CFR Part 11, FISMA and HIPAA compliant and will be used to store both identifiable and de-identifiable information. When clinicians use a hypothermia protocol, data including vitals, temperature, laboratory values and medications issued are routinely collected. These variables are what we will collect for this study; therefore, the variables will exist in the EMR system. IRB approved researchers assigned to this study will be assigned this REDCap project by the Research Director. Variable collection and completion of electronic case reports forms will be conducted without the need to write on paper and they can be transferred directly from EMR to REDCap project electronic case report forms. One enrollment log will be created on paper and stored in the Principal Investigator's office. This office is protected by a door with a lock requiring key access only available to the PI. In addition, this office is located in a wing that is secure and accessible only to Northwell Health employees with authorized key card access; these patients' names will be entered into the demographic electronic case report form with two identifier: MRN number and name. There will be no other identifiers stored in the database. Once the analysis is complete, the two identifiers will be removed and the de-identified data will remain in REDCap for the length outlined for this study.

# 10.1.4 FUTURE USE OF STORED SPECIMENS AND DATA

Data collected for this study will be analyzed and stored at the North Shore University Hospital of Northwell Health. After the study is completed, the de-identified, archived data will be transmitted to and stored at the North Shore University Hospital, Department of Cardiothoracic Surgery, for use by other researchers including those outside of the study. Permission to transmit data to the <specify name of Data Repository> will be included in the informed consent.

When the study is completed, access to study data and/or samples will be provided through the Department of Cardiothoracic Surgery, Northwell Health.

# 10.1.6 SAFETY OVERSIGHT

Safety oversight will be under the direction of a Data and Safety Monitoring Board (DSMB) composed of individuals with the appropriate expertise, including clinical research regulatory experience and clinical experience using hypothermic protocols on patients in a critical care setting and/or in the operating room. Members of the DSMB should be independent from the study conduct and free of conflict of interest, or measures should be in place to minimize perceived conflict of interest. The DSMB will meet at least at four time points during this pilot study to assess safety and efficacy data. The DMSB will operate under the rules of an approved charter that will be written and reviewed at the organizational meeting of the DSMB. At this time, each data element that the DSMB needs to assess will be clearly defined. The DSMB will provide its input to the Principal Investigator and lead regulatory coordinator who will then report it to the IRB of record.

#### 2. Infection:

Monitoring: CBC every 12 hours.

Actions:

- If there is culture evidence of systemic bacterial infection at screening, subject will not be enrolled.
- If patient develops a systemic bacterial infection at any time during hypothermia, subject will be taken off hypothermia and re-warming will be initiated to achieve systemic temperature of 37°C. Antibiotics will be administered as per ICU standard of care.
- 3. Arrhythmias:
  - Monitoring: Continuous cardiac telemetry and arterial blood pressure monitoring as per ICU standard of care

Actions:

- o If subject has uncontrolled cardiac arrhythmia at screening, subject will not be enrolled.
- If the subject develops hemodynamically unstable arrhythmia or severe bradycardia (<

   40 beats per minute) during the study, subject will be taken off hypothermia and re-warming will be initiated to achieve systemic temperature of 37°C. Arrhythmias will be treated as per ICU standard of care.
- **4.** Electrolyte abnormalities:

Monitoring: Basic metabolic profile, magnesium, phosphorus every 12 hours Actions:

- If subject has uncorrected electrolyte abnormalities at screening, subject will not be enrolled.
- Any electrolyte abnormalities will be corrected as per ICU standard of care protocol during the hypothermia protocol. In the event the electrolyte abnormalities are

refractory to therapy, the subject will be taken off hypothermia and re-warming will be initiated to achieve systemic temperature of 37°C.

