### 5 STUDY POPULATION

### 5.1 INCLUSION CRITERIA

In order to be eligible to participate in this study, an individual must meet all of the following criteria:

- 1. Provision of signed and dated informed consent form from Legally Authorized Representative.
- 2. Stated willingness to comply with all study procedures and availability for the duration of the study
- 3. Male or female, aged 18 years or above
- 4. COVID positive
- 5. On mechanical ventilation with either: refractory respiratory acidosis (ph  $\leq$  7.20), hypercarbia (pCO2  $\geq$  55 mmHg), refractory hypoxia (pO2/FIO2 <150), or plateau pressures >30

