## 5.2 EXCLUSION CRITERIA

An individual who meets any of the following criteria will be excluded from participation in this study:

- 1. Bleeding (active bleeding, platelets less than 50,000)
- 2. Uncontrolled cardiac arrhythmia
- 3. History of cryoglobulinemia, major trauma, pregnancy
- 4. Active non-COVID-19 infection that is not controlled with antibiotic or antifungal regimen

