# 7.2 PARTICIPANT DISCONTINUATION/WITHDRAWAL FROM THE STUDY

Participants are free to withdraw from participation in the study at any time upon request. An investigator may discontinue or withdraw a participant from the study for the following reasons:

- If any clinical adverse event (AE), laboratory abnormality, or other medical condition or situation occurs such that continued participation in the study would not be in the best interest of the participant
- Disease progression which requires discontinuation of the study intervention
- If the participant meets an exclusion criterion (either newly developed or not previously recognized) that precludes further study participation
- Participant unable to receive hypothermia protocol for 48 hours

The reason for participant discontinuation or withdrawal from the study will be recorded on the Study Withdrawal Case Report Form (CRF).

The hypothermia protocol will be discontinued and full rewarming will be initiated prior to 48 hours if the following conditions occur: (1) hemodynamically unstable arrhythmia, (2) severe bradycardia (< 40bpm), (3) MAP less than 60mm Hg while on more than one vasopressor after resuscitation, (4) severe bleeding.

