# 8.3.4 TIME PERIOD AND FREQUENCY FOR EVENT ASSESSMENT AND FOLLOW-UP

The principal investigator and investigators on the study will review labs and vitals continuously and as outlined in the protocol. The patients are monitored in a critical care unit; as per standard of care, vitals are documented and monitored continuously. The occurrence of an adverse event (AE) or serious adverse event (SAE) may come to the attention of study personnel during the course of treatment.

All AEs including local and systemic reactions not meeting the criteria for SAEs will be captured on the appropriate case report form (CRF). Information to be collected includes event description, time of onset, clinician's assessment of severity, relationship to study product (assessed only by those with the training and authority to make a diagnosis), and time of resolution/stabilization of the event. All AEs

occurring while on study must be documented appropriately regardless of relationship. All AEs will be followed to adequate resolution.

Any medical condition that is present at the time that the participant is screened will be considered as baseline and not reported as an AE. However, if the study participant's condition deteriorates at any time during the study, it will be recorded as an AE.

Changes in the severity of an AE will be documented to allow an assessment of the duration of the event at each level of severity to be performed. AEs characterized as intermittent require documentation of onset and duration of each episode.

The study coordinator will record all reportable events with start dates occurring any time after informed consent, during hypothermic protocol and through full rewarming. The principal investigator will review all AE and SAE in a timely manner to determine severity and relation to study intervention.

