#### 9.2 SAMPLE SIZE DETERMINATION

N/A – this is a pilot study and the study team will enroll 20 subjects. The study will make 20 attempts, meaning 20 patients will be enrolled and the intervention attempted; if any patients withdraw prior to the completion of the intervention, they will not be replaced.

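### The entry rules are split across sections that do not agree: 10.1.6 and 8.3.3.1 bar electrolyte and infection cases that pass the 5.1/5.2 checklist, and no entry criterion addresses the blood-pressure stopping condition in 7.2

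*Combined protocol and SAP*

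**What the plan says.** Section 5.1 sets necessary conditions: "In order to be eligible to participate in this study, an individual must meet all of the following criteria". Section 5.2 then states: "An individual who meets any of the following criteria will be excluded from participation in this study". Its five items are bleeding or low platelets; uncontrolled arrhythmia; a history item (cryoglobulinemia, major trauma, pregnancy); non-COVID infection that treatment has not controlled; and conditions that spoil indirect calorimetry. The fifth item has run into the heading of 5.3 in the text available, and I count it as part of 5.2. Neither section mentions electrolytes, blood pressure or vasopressors.

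Section 10.1.6, under its list of risks and protections, adds enrolment bars of its own. The one for electrolytes reads: "If subject has uncorrected electrolyte abnormalities at screening, subject will not be enrolled". The one for infection bars anyone with culture evidence of systemic bacterial infection at screening. Section 8.3.3.1, in the text on grading infections, says that patients with active bacterial or fungal infection on top of COVID-19 are excluded.

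Section 7.2 lists four conditions under which cooling stops before 48 hours. The third is "MAP less than 60mm Hg while on more than one vasopressor after resuscitation". Section 9.2 fixes enrolment at 20 attempts and says that "if any patients withdraw prior to the completion of the intervention, they will not be replaced".

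**The concern.** An enrolment rule works only if the person screening the patient sees it. The schema in 1.2 tells staff to screen by the inclusion and exclusion criteria, and the Schedule of Activities in 1.3 has a single inclusion/exclusion line. Nothing there points to 10.1.6 or 8.3.3.1. Staff who follow the instructions exactly can enrol and cool a patient whom another section forbids. Section 10.1.6 names electrolyte abnormalities and infections among the study's primary concerns and describes the study as a major increase above minimal risk, so these are not peripheral rules. Such an enrolment would also be noncompliance with the protocol, to be handled as a deviation under 10.1.10.

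The blood-pressure issue differs in kind. If a patient already meets the third condition in 7.2 before cooling, the plan does not say whether that patient may start or, having started, must be rewarmed at once.

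**Working it through.** No formula applies to the main point; the check sets the lists side by side.

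**Step 1. The four enrolment bars in 10.1.6 against 5.2**

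| Bar in 10.1.6 | Counterpart in 5.2 | Result |
|---|---|---|
| Active bleeding | Item 1, "Bleeding (active bleeding, platelets less than 50,000" | Covered |
| Uncontrolled arrhythmia | Item 2, "Uncontrolled cardiac arrhythmia" | Covered |
| Culture-evidenced systemic bacterial infection | Item 4, limited to uncontrolled infection | Partly covered |
| Uncorrected electrolyte abnormality | None | Absent |

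Two of the four bars are covered, one partly and one not at all.

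**Step 2. Infection across three sections.** Take a patient with a culture-proven systemic bacterial infection controlled by antibiotics. Item 4 of 5.2 does not exclude this patient; 10.1.6 does; 8.3.3.1 does if the infection still counts as active. Now take a patient with an active fungal infection controlled by an antifungal. Item 4 does not exclude this patient, the bacterial bar in 10.1.6 does not reach the case, and 8.3.3.1 treats the patient as excluded. The three rules have three different scopes.

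**Step 3. The four stopping conditions in 7.2 against 5.2**

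| Condition in 7.2 | Counterpart at entry |
|---|---|
| Hemodynamically unstable arrhythmia | Plausibly item 2 |
| Bradycardia below 40 bpm | Only if read as an uncontrolled arrhythmia |
| MAP below 60 mm Hg on more than one vasopressor | None |
| Severe bleeding | Item 1 |

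**Step 4. Is there a backstop?** Section 7.2 lets the investigator withdraw a participant who is later found to meet an exclusion criterion. Electrolytes and blood pressure are not in 5.2, so that route does not reach them through the list. The general clause in 7.2 on the participant's best interest does remain available.

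**Step 5. Can the rules be applied with data already collected?** Section 1.3 schedules the basic metabolic panel, magnesium, phosphorus, vital signs and concomitant medication at screening/baseline. Electrolyte, blood-pressure and vasopressor information is therefore to hand. Cultures are not scheduled, so the source of culture evidence is left open.

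**Step 6. Scale.** With 20 enrolled and no replacement (9.2), and all enrolled patients used in all analyses (9.3), one affected patient is 1/20 = 5% of the sample. This is the weight of one patient. It says nothing about how likely such a patient is.

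**The case against.** The strongest reply is that nothing here is a contradiction in logic. Section 5.1 gives necessary conditions and 5.2 gives grounds for exclusion; neither says that everyone else must be enrolled. Section 10.1.6 simply adds bars, and a patient who satisfies every section can be found. There is one site, the electrolyte tests are scheduled at screening, and 10.1.6 has the principal investigator notified of abnormal results so that its measures are carried out. This stands as far as it goes: the lists can be satisfied jointly, and the risk of divergence at a single site is limited. It does not remove the defect, because the screening instructions point only to the inclusion and exclusion criteria, and no one can apply the electrolyte bar consistently while *uncorrected* is undefined.

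On blood pressure the reply is stronger. Section 7.2 speaks of conditions that *occur*, which can be read as onset during cooling, and 10.1.6 speaks of a patient who develops an infection or arrhythmia. On that reading 7.2 and 5.2 do not conflict. I accept this: the issue is an omission, and what remains is that the text does not settle the reading.

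Three stronger inferences are tempting and unsupported:

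- **That the electrolyte bar would shut out many hypercarbic patients through raised bicarbonate.** The documents do not name bicarbonate as an electrolyte that counts, give no reference range, and give no distribution of pH or pCO2 among candidates.
- **That the DSMB would be misled.** Section 8.3.4 does say: "Any medical condition that is present at the time that the participant is screened will be considered as baseline and not reported as an AE". But deterioration is recorded, the report to the DSMB under 10.1.6 covers actions taken, and 7.2 puts reasons for withdrawal on a case report form.
- **That an early stop leaves no data.** Section 7.1 asks for calorimetry, blood gases and laboratory tests at discontinuation, and for the remaining procedures to be completed.

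**Conclusion.** The point holds as an inconsistency between sections that bears on who is enrolled. The electrolyte bar in 10.1.6 is missing from 5.1/5.2 and undefined, and infection has three differing rules in 5.2, 8.3.3.1 and 10.1.6. As written, a patient can pass the checklist and be cooled although the safety section forbids enrolment. For blood pressure the conclusion is narrower: the plan is silent on a 7.2 stopping condition already present before cooling, and this should not be read as a direct conflict.

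The size is 5% of the sample per affected patient. The documents give no screening frequencies, so neither the expected number nor any effect on the results can be estimated. The conclusion assumes that staff screen by the criteria as 1.2 and 1.3 direct, and that 10.1.6 is meant to bind enrolment, which its wording supports. The correction should be made because it concerns risks that the protocol itself ranks as primary.

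**What to change.** Make one list govern entry.

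- **Electrolytes.** Reconcile 5.2 with 10.1.6. Either carry the bar into 5.2 in defined terms (which analytes, and what *uncorrected* means) or remove it from 10.1.6.
- **Infection.** Reconcile 5.2, 8.3.3.1 and 10.1.6 so that all three state the same rule. If culture evidence is part of it, say where that evidence comes from.
- **Blood pressure.** Reconcile 5.2 with 7.2 by stating whether *occur* means new onset only, and how a stopping condition already present before cooling is handled.

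Which clinical rule and threshold applies in each case is for the sponsor and investigator to decide.

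The cost is wording in these sections and a matching update to the screening checklist. The electrolyte and blood-pressure information is already collected at screening/baseline. The one downside is that a few more screened patients may fail screening, depending on the rules chosen.
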